2.2.4 Sample Size Determination

A total of five treatment groups and approximately 160 participants are planned. Each placebo group will include 20 randomly allocated participants, and each SLN360 group will include 40 randomly allocated participants. This will result in a total of 120 participants exposed to SLN360 and 40 participants exposed to placebo. The placebo groups will be analysed and reported both separately and in combination.

The treatment effect observed in the first-in-human (FIH) Phase 1 study (APOLLO; ClinicalTrials.gov identifier NCT04606602; EudraCT identifier 2020-002471-35) between placebo and 300 mg SLN360 at Day 150 (the smallest effect observed at the lowest dose to be used in the proposed study) was approximately 60% with a conservative pooled standard deviation of 40%. As few as 10 participants per arm would give approximately 90% power to detect this magnitude of difference, at the 5% significance level ($p <0.05$).

The proposed sample size, even separating the placebo arms with a different dose frequency, is expected to be more than adequate to demonstrate the SLN360 effect on Lp(a). The larger sample size should allow a more robust evaluation of safety at these doses and dose frequencies than a smaller sample size that may be expected in a Phase 2 study.

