3.1.6 Hypothesis Testing

To demonstrate the treatment effect of SLN360 compared with placebo, the following hypothesis:

$$H_0: \mu_T = \mu_P$$

will, at the 5% significance level, be tested against the alternative hypothesis:

$$H_1: \mu_T > \mu_P$$

wherein μ denotes the mean time-averaged change in Lp(a) from Day 1 pre-dose to Week 36, T denotes SLN360 and P denotes placebo. For estimating treatment effects, the difference between treatments and corresponding confidence intervals will be provided.

No formal statistical hypothesis testing is planned for safety data.

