3.1.8 Handling of Dropouts and Missing Data

Missing data will not be imputed unless otherwise specified. Only observed data will be used in the summaries and analyses.

In all listings, missing or incomplete dates should be left as they have been recorded. However, for calculation / sorting / assignation based on dates, the following methods will be used:

- 1) The most conservative approach will be systematically considered (i.e. if the onset date of an AE is missing / incomplete, it is assumed to have occurred during the active phase (i.e. a TEAE for AEs) except if the partial onset date or other data [stop date, ...] indicates differently).
- 2) A missing/incomplete date of medical history or disease diagnosis will be assumed to have occurred before any study treatment.
- 3) If a partial date and the associated information do not allow to state about the assignation to a group / category, all the possible groups / categories will be considered (i.e. an AE could be assigned to several possible doses at event onset according to its partial onset date and stop date. Particularly an AE with missing start date will be assigned to each dose received before its end date.).
- 4) Where this is possible, the derivations based on a partial date will be presented as superior inequalities (i.e.: for an AE started in FEB2004 after the administration performed on 31JAN2004, the days since last dose will be “ ≥ 2 ”, similarly the duration of ongoing AEs or medication will be “ $\geq xx$ ” according to the start and last visit dates).

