3.4.2 Secondary Pharmacodynamics and Efficacy Endpoints

Time averaged secondary endpoints will be calculated and analyzed using the same conventions as the primary endpoint.

For each PD parameter, percent and absolute change from Day 1 pre-dose to each visit will be summarized descriptively. The least squares means, standard errors, and 2-sided 95% confidence intervals from analysis of variance will be provided for each treatment group and for the pairwise comparisons of each SLN360 group and placebo. Figures displaying mean (+/- standard deviation) by visit will be plotted for Lp(a), Apolipoprotein B, LDL Cholesterol, HDL Cholesterol, Total Cholesterol, Triglycerides, Oxidized Phospholipids, and C Reactive Protein will be displayed at baseline and each post-baseline visit. Additionally, figures for mean change and percent change (+/- standard deviation) from baseline will be presented for Lp(a), Apolipoprotein B, LDL Cholesterol, and C Reactive Protein will be displayed for each post-baseline visit.

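### By-visit change is read as an observed-case ANOVA at each visit; a repeated-measures model would cheaply reduce late-visit bias if dropout is related to earlier response

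*SAP*

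**What the plan says.** For each pharmacodynamic parameter, SAP 3.4.2 states that "percent and absolute change from Day 1 pre-dose to each visit will be summarized descriptively". It adds least squares means, standard errors and two-sided 95% intervals "from analysis of variance will be provided for each treatment group" and for each SLN360 group against placebo. SAP 2.3.2.2 lists by-visit percent and absolute change as secondary endpoints, and the visit table in SAP 3.1.2 has 13 post-baseline visits, from Week 1 to Week 60.

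On missing values, SAP 3.1.8 imputes nothing unless otherwise specified and continues: "Only observed data will be used in the summaries and analyses". The only ANOVA whose terms are given (SAP 3.4.1, primary endpoint) has treatment as its single factor. Neither document names a visit term, a within-person covariance, a baseline covariate or a missing-data sensitivity analysis for the by-visit results. Protocol 12 says the SAP will contain the procedures for missing data, and Protocol 12.4.5 leaves imputation to the SAP.

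The SAP does not say in so many words that a separate ANOVA is fitted at each visit. That is inferred from these sections together, and it is the natural reading.

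**The concern.** Protocol 1.2 sets the trial's aim as the greatest magnitude and duration of Lp(a) lowering with the lowest dosing frequency. Duration is read largely from the late visits (Weeks 40, 48 and 60), which is also where missing values accumulate. A visit-wise observed-case analysis averages over those who remain. If participants whose Lp(a) had already rebounded are more likely to be missing, the remaining average looks more durable than it is. The earlier values that would reveal this are in the database but are not used.

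Arm-level means are themselves a planned output, so bias in them matters even where it cancels in the comparison with placebo.

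**Working it through.** **Inputs from the documents.** The level is 5% (SAP 3.1.6: "will, at the 5% significance level, be tested against the alternative hypothesis"), and the intervals are two-sided (SAP 3.4.2). SAP 2.2.4 gives the planning effect, which "was approximately 60% with a conservative pooled standard deviation of 40" percentage points, and the allocation: "Each placebo group will include 20 randomly allocated participants, and each SLN360 group will include 40 randomly allocated participants". With placebo pooled, as in SAP 3.4.1, each comparison is 40 against 40.

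**Inputs assumed.** The documents give no dropout rate, between-visit correlation or dropout mechanism. I used 5, 10 and 20% missing by Week 60, correlation 0.7 (range 0.3 to 0.9), and log-odds of dropout rising by 1 per SD of poorer response at the previous visit. The Phase 1 Day 150 SD of 40 is carried over to Week 60.

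**1. The plan's own figure.** SAP 2.2.4 says "As few as 10 participants per arm would give approximately 90% power to detect this magnitude of difference". SE = 40 × √(2/10) = 17.9, and 60/17.9 = 3.35. Power = Φ(3.35 − 1.96) = 91.8%; the noncentral t gives 88.7%. The stated figure reproduces.

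**2. Precision at full enrolment.** SE = 40 × √(1/40 + 1/40) = 8.94, so the 95% half-width is about 17.7 points. Power for a 60-point effect exceeds 99.9%.

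**3. Bias of an observed-case mean.** If a fraction p is missing and the missing participants' true change is on average m points worse than their arm's mean, then

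bias = −m × p/(1 − p).

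**4. Simulation at Week 60.** Four arms of 40 (pooled placebo and three active), 13 visits, true difference −60, 4,000 replicates. Observed-case ANOVA is compared with the maximum-likelihood repeated-measures estimate (treatment-by-visit means, unstructured covariance). Missing at random (MAR), dropout in active arms only, correlation 0.7:

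| Missing | ANOVA bias, difference | Repeated-measures bias | ANOVA 95% coverage | SE ratio (repeated-measures/ANOVA) |
|---|---|---|---|---|
| 5% | −1.2 | 0.2 | 94.6% | 0.998 |
| 10% | −2.9 | 0.0 | 94.1% | 0.994 |
| 20% | −5.5 | 0.1 | 90.5% | 0.985 |

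Negative bias means lowering is overstated. In SD units the ANOVA bias is 1.2/40 = 0.03, 2.9/40 = 0.07 and 5.5/40 = 0.14, so it shrinks in proportion if the true SD is smaller.

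**5. What step 4 assumes in plain terms.** The simulated active-arm mean biases were −1.33, −2.87 and −5.54. Inverting step 3, m = 1.33 × 0.95/0.05 = 25, 2.87 × 0.90/0.10 = 26 and 5.54 × 0.80/0.20 = 22 points. The scenario therefore needs missing participants to be about 22 to 26 points worse than their arm's average.

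**6. Check on coverage at 20%.** SE = 40 × √(1/32 + 1/40) = 9.49, and 5.49/9.49 = 0.58. Φ(1.96 − 0.58) − Φ(−1.96 − 0.58) = 0.916 − 0.006 = 91%, in line with the simulated 90.5%.

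**7. Other mechanisms.**
- Complete data: the two estimates are identical (no baseline term in either).
- Same response-related mechanism in all arms, 20%: ANOVA arm means are biased by −5.7, but the difference by only −0.1.
- Completely random dropout: neither analysis is biased. SE ratio 0.983, 0.968 and 0.936 at 5, 10 and 20% with correlation 0.7; at 20% it runs from 0.963 (correlation 0.5) to 0.914 (correlation 0.9).
- Missing not at random (MNAR), 20% in active arms, log-odds 2 per SD of the current value, correlation 0.3-0.7: ANOVA bias −4.9 to −8.7, repeated-measures bias −1.5 to −2.3, SE ratio about 1.00-1.01.

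**The case against.** Three stronger readings are tempting, and none is supported.

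- A reader might infer that the planned analysis is unbiased only if values are missing completely at random. For the treatment difference that is too strong: response-related dropout acting alike in every arm left it biased by only 0.1 point.
- A reader might infer that a repeated-measures model removes dropout bias outright. It does so only under missing at random with a correctly specified model; 1.5 to 2.3 points remained in the MNAR cases.
- A reader might infer that late-visit intervals become clearly tighter. The 2-9% fall in SE appears under random dropout, where ANOVA is already unbiased. Where the bias arises, the fall is about 0-2%.

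The case against acting has further force. No document shows that weak responders leave. Participants and investigators are blinded (Protocol 4.1.2), Lp(a) is measured centrally (Protocol 6.4), and poor Lp(a) response is not a listed reason for withdrawal (Protocol 10.2.2 and 10.2.3). Conduct already limits missing data: stopping drug is not withdrawal of consent (Protocol 4.2), and assessments continue where possible (Protocol 9.3, 10.2.2, 10.2.3). By-visit results lie outside the Holm procedure, and duration is also assessed by time-averaged change to Weeks 48 and 60.

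The simulation also has limits. It contained no treatment discontinuation, baseline terms or Kenward-Roger adjustment. Someone who leaves after missing a later dose would be predicted largely from participants who received it, so the model can also overstate durability under a treatment policy strategy.

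All of this stands, and it keeps the point small. It does not show that the planned analysis is preferable: with complete data nothing is lost, and with missing data the model needs a weaker assumption and uses the same observed values.

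**Conclusion.** The point holds in a limited, conditional form. As naturally read, the by-visit analysis makes no use of earlier values, so response-related dropout biases late-visit arm means, and also the SLN360-placebo differences when the dropout pattern differs between arms.

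Under the assumed conditions (5-20% missing by Week 60, confined to active arms, SD 40, correlation 0.7), the Week 60 difference is overstated by about 1 to 6 points. That compares with a 60-point planning effect and a half-width of about 18 points. Rate, correlation and mechanism are all assumptions.

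No conclusion about whether SLN360 lowers Lp(a) depends on this. It bears on the reported size and durability of effect at Weeks 40-60, and possibly on smaller effects on LDL-C and apoB, for which the documents give no SD.

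**What to change.** In SAP 3.4.2, for Lp(a), LDL-C and apoB at the visits where each is scheduled, make the by-visit analysis a mixed model for repeated measures:

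- fixed effects for treatment, visit, treatment-by-visit and baseline-by-visit;
- unstructured covariance, with a simpler structure stated in advance in case of non-convergence (13 visits in about 160 participants makes this necessary);
- Kenward-Roger degrees of freedom;
- all observed values included, also those after drug discontinuation.

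Report least squares means and contrasts at each visit, and keep the visit-wise ANOVA as a check. The baseline-by-visit term is a covariate adjustment in its own right, so the two analyses need not agree exactly even with complete data. Record and justify the change in SAP section 6, which now reports no departures from the protocol, because Protocol 12.4 and 12.4.4.1 specify analysis of variance.

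The cost is SAP text, some programming and the covariance fallback. The remaining weakness is reliance on missing at random for participants who leave after stopping drug, which the SAP should acknowledge.

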3.4.3 Exploratory Endpoints

Analysis of exploratory endpoints, the pharmacogenetic effects of germline genetic variation on response to SLN360, measured by association analysis of genetic variants with markers of SLN360 efficacy, including change in Lp(a), will be described in a separate analysis plan.

3.4.4 Subgroups

There is no planned subgroup analysis.

3.5 Safety Assessment

All safety data will be included in the subject data listings. Safety data will be summarised by actual treatment received (and in total for selected analyses) based on the Safety Population.

3.5.1 Adverse Events (AEs)

All AEs will be coded to system organ class and preferred term using MedDRA. Treatment emergent adverse events (TEAEs) are defined as AEs that start after the first dose of study drug. Severity will be graded according to the National Cancer Institute Common Terminology Criteria for Adverse Events (NCI-CTCAE) on a five-point scale (Grade 1 to 5). Study drug-related AEs are defined as AEs considered by the investigator as having a reasonable possibility of being related to study drug.

An overview of TEAEs will be provided including counts and percentages of subjects (and event counts) with the following:

- Any TEAEs (overall and by maximum severity)
- Any study drug-related TEAEs (overall and by maximum severity)
- Any serious adverse events (SAEs)
- Any serious TEAEs
- Any study drug-related serious TEAEs
- Any TEAEs leading to discontinuation of study drug
- Any TEAEs leading to discontinuation of study
- Any TEAEs leading to death

Summary tables of TEAEs, TEAEs by maximum severity, study drug-related TEAEs, serious TEAEs and TEAEs leading to discontinuation of study drug or study will be provided with the number and percentage of subjects with adverse events and the number of events classified by primary system organ class, and preferred term.

System organ classes and preferred terms will be sorted alphabetically.

For tabulations that include classification by relationship to study drug, TEAEs with missing relationship will be considered related to study drug. For tabulations that include classification by severity, missing severity will be considered as the most severe TEAEs that are not SAEs.

Adverse event listings will be presented by subject, system organ class and preferred term.

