6.5. Safety Procedures

6.5.1. Adverse Event Assessments

Information regarding the occurrence of AEs for each participant will be collected from the time a signed and dated ICF for the main study is obtained until completion of the participant's last study-related procedure, which may include contact to follow-up for safety. Adverse events that start from the time the participant signs the main study ICF until treatment administration on Day 1 will be assigned as non-treatment emergent AEs; AEs starting or worsening after treatment administration will be recorded as TEAEs. See the Time and Events tables ([Appendix 15.1](#) and [Appendix 15.2](#)) for detailed timing of assessments. Grading of AEs is outlined in [Section 11.2](#).

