11. ADVERSE EVENTS AND SERIOUS ADVERSE EVENTS

11.1. Definitions

11.1.1. Adverse Events

An AE is any untoward medical occurrence associated with the use of a drug/investigational drug in humans, whether or not considered drug related. An AE can therefore be any unfavourable and unintended sign, symptom or disease that either emerges during the study or, if present at screening, worsens during the study, regardless of the suspected cause of the event.

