11.3. Safety Reporting

11.3.1. Reporting Adverse Events

All medical and psychiatric conditions (except those related to the indication under study) present at screening will be documented in the medical history eCRF. Changes in these conditions and new symptoms, physical signs, syndromes or diseases should be noted on the eCRF during the rest of the study. Clinically significant laboratory abnormalities should also be recorded as AEs.

Wherever possible, a specific disease or syndrome rather than associated signs, symptoms, or abnormal assessments or laboratory findings should be identified by the Investigator and recorded on the eCRF. However, if an observed or reported sign or symptom is not considered a component of a specific disease or syndrome by the Investigator, it should be recorded as a separate AE on the eCRF.

Surgical procedures not prohibited in the eligibility criteria that were planned before enrolment in the study are not considered AEs, if the conditions were known before study inclusion. The medical condition(s) necessitating the surgical procedure should be reported in the patient's medical history.

Each AE is to be documented on the eCRF with reference to the date of onset, duration, frequency, severity, relationship to study drug, action taken with study drug, treatment of event and outcome. Furthermore, each AE is to be classified as being serious or non-serious. Changes to AEs and resolution dates are to be documented on the eCRF.

When changes in the intensity of an AE occur more frequently than once a day, the maximum intensity for the event should be noted. If the intensity category changes over time, then those changes should be recorded separately (with distinct onset dates).

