12. DATA ANALYSIS AND STATISTICAL CONSIDERATIONS

The database will be locked and the main analysis will be performed after all participants have completed 36 weeks of treatment. All follow-up data collected up to Week 60 will be analysed subsequently and included in the final report.

Study Number: SLN360-002	Compound No.: SLN360
Protocol	Version: 1.0

Prior to the database lock (either at main or final analysis), a detailed, finalised Statistical Analysis Plan (SAP) will be completed, approved and placed on file. The SAP will contain a more comprehensive description of the statistical analyses methodology for the study than outlined in this Protocol. The SAP will provide full details of the analyses, the data displays and the algorithms to be used for data derivations, database closure and unblinding of the randomisation code. The SAP will also contain the rules and data handling conventions that will be used to perform the analyses and the procedure(s) that will be used to account for missing data. Any change to the analysis methods described in the Protocol will be documented in the SAP and/or Clinical Study Report (CSR) along with the justification for making the change. Additional exploratory analyses performed after the database lock that are not described in the SAP can be conducted as deemed appropriate. These additional analyses will be fully identified as exploratory post-hoc analyses in the CSR.

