12.4.4.2.1. Adverse events

The verbatim terms used in the eCRF by Investigators to identify AEs will be coded using MedDRA. All reported AEs with onset during the treatment phase will be included in the analysis and will be summarised by treatment group, and these include the following: AEs that have worsened since study entry, TEAEs, study drug-related TEAEs, serious TEAEs, study drug-related serious TEAEs, TEAEs leading to study discontinuation, TEAEs leading to discontinuation of study treatment or TEAEs leading to death. All other AEs will be listed only.

For each AE, the number and percentage of participants who experience at least one occurrence of the given event will be summarised by treatment group. Summaries will be presented overall and also by system organ class and preferred term using MedDRA. TEAEs will also be summarised by severity and relationship classified by System Organ Class and Preferred Term.

Study Number: SLN360-002	Compound No.: SLN360
Protocol	Version: 1.0

The number and percentage of early withdrawals and the corresponding reasons will be tabulated presenting number and percentage of participants for each treatment group.

Summaries, listings, datasets or narratives may be provided, as appropriate, for those participants who die, discontinue treatment due to an AE or experience a severe or serious AE.

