6 CHANGES FROM PROTOCOL-SPECIFIED STATISTICAL ANALYSES

There are no changes from the protocol-specified statistical analyses.

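### The SAP defines treatment-emergent AEs by start date only and omits the protocol's worsened-AE summary, yet declares no changes from the protocol; the effect is small and confined to descriptive safety tables

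*SAP*

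**What the plan says.** The protocol deals with treatment emergence in two places. Section 6.5.1 classes AEs that start between main-study consent and dosing on Day 1 as not treatment-emergent, and continues: "AEs starting or worsening after treatment administration will be recorded as TEAEs". Section 12.4.4.2.1, in the statistics chapter, lists the AE categories to be summarised by treatment group, and the first is "AEs that have worsened since study entry".

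SAP 3.5.1 is narrower: "Treatment emergent adverse events (TEAEs) are defined as AEs that start after the first dose of study drug". Its overview and its tables by system organ class and preferred term contain no worsened-AE category.

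Protocol Section 12 allows analysis methods to change, provided the change and its justification are documented in the SAP and/or the clinical study report. SAP Section 6 reads: "There are no changes from the protocol-specified statistical analyses".

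Two other protocol rules decide how much this matters. Section 11.1.1 defines an AE as something that "either emerges during the study or, if present at screening, worsens during the study". Section 11.3.1 governs recording: "If the intensity category changes over time, then those changes should be recorded separately (with distinct onset dates".

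**The concern.** The two documents give different rules for the same term, and the SAP is the one that will be programmed. Under an onset-only rule, an AE that began during screening and worsened after dosing would keep its pre-dose start date and stay out of the treatment-emergent tables, although the protocol counts it. Such events can occur: AEs are collected from main-study consent, and screening may begin up to 28 days before the first dose.

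Safety and tolerability form a named secondary objective, and most of the SAP's AE overview rests on this one definition. A reader of the SAP is also told that nothing differs from the protocol. That is inaccurate at least for the missing summary, which the protocol's own statistics section names.

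**Working it through.** No figure in the plan bears on this point, so the check is a comparison of text and a count of categories.

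**Step 1. Count the categories.** Inputs: the list in Protocol 12.4.4.2.1 and the overview list in SAP 3.5.1.

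| Category | Protocol 12.4.4.2.1 | SAP 3.5.1 overview |
|---|---|---|
| Worsened since study entry | yes | **no** |
| TEAEs | yes | yes |
| Drug-related TEAEs | yes | yes |
| Serious TEAEs | yes | yes |
| Drug-related serious TEAEs | yes | yes |
| TEAEs leading to study discontinuation | yes | yes |
| TEAEs leading to treatment discontinuation | yes | yes |
| TEAEs leading to death | yes | yes |
| All SAEs | no | yes |

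Each list has 8 entries and 7 are shared. The protocol has 8 − 7 = 1 category with no SAP counterpart (worsened AEs), and the SAP has 8 − 7 = 1 of its own (all SAEs). Seven of the eight SAP rows depend on the TEAE definition.

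**Step 2. Look for the missing part elsewhere in the SAP.** The only other text that settles treatment emergence is the incomplete-date rule in SAP 3.1.8, which also works from onset date alone. Nothing restores worsening.

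**Step 3. Follow a pre-existing event through both rules.** Protocol 6.5.1 does not define worsening. Becoming serious is treated here as worsening, which is an assumption.

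| Course after first dose | Protocol 6.5.1 | SAP 3.5.1, with records kept as in Protocol 11.3.1 |
|---|---|---|
| Condition present at screening worsens | TEAE | TEAE: the worsening is itself an AE (11.1.1) |
| Pre-dose AE rises in grade | TEAE | TEAE: new record with post-dose onset |
| Pre-dose AE becomes serious, grade changes | TEAE | TEAE, for the same reason |
| Pre-dose AE becomes serious, grade unchanged | TEAE | **Not a TEAE**: onset stays before dosing |
| Pre-dose AE worsens within its grade | TEAE | **Not a TEAE**, and no dated record is described |
| Pre-dose AE improves in grade | Not a TEAE | **TEAE**: new record with post-dose onset |

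The fourth row arises because seriousness is recorded separately from intensity: "each AE is to be classified as being serious or non-serious". The rule on separate records is triggered by intensity category only. Such an event still reaches the all-SAE overview row and the listings. It is missing from the serious-TEAE rows and from the serious-TEAE table by system organ class and preferred term; no such table is planned for all SAEs.

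The last row arises because the recording rule does not depend on direction. A fall in grade also produces a record with its own onset date, and a rule that looks only at onset will count it.

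**The case against.** The strongest reply is that the recording rule already does the work. If every change of intensity category has its own onset date, a post-dose rise in grade is a post-dose start, and the two definitions differ in wording more than in output. Most of this stands. A reader might infer from SAP 3.5.1 that worsened AEs in general disappear from the TEAE tables; Protocol 11.1.1 and 11.3.1 do not support that.

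The residue of AEs that become serious is also thin. The fallback grading scale in Protocol 11.2.1, for AEs not listed in CTCAE, ties hospitalisation to Grade 3, life-threatening consequences to Grade 4 and death to Grade 5. Becoming serious by one of those routes will usually change the grade. What remains is chiefly an AE already at Grade 3, or an important medical event without a grade change. Within-grade worsening has no dated record in the documents, so a new definition would recover little of it.

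A further reply is that the worsening wording sits in the protocol's assessment section, that Protocol 12.4.4.2.1 itself starts from onset during the treatment phase, and that changes may be documented in the study report. This makes the charge against SAP Section 6 arguable as regards the definition. It does not answer the missing summary, which Protocol 12.4.4.2.1 names outright.

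A reader might also infer from that treatment-phase phrase that follow-up AEs drop out of the SAP tables. The SAP definition has no end date, and SAP Section 5 has data to Week 60 analysed, so the documents do not support that either.

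The objection leaves the improvement case untouched. The rule that rescues most worsened events is the one that turns an improving pre-dose event into a TEAE.

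**Conclusion.** The point holds as a minor discrepancy. The SAP's TEAE definition is narrower than Protocol 6.5.1, one of eight protocol AE categories has no SAP display, and the SAP's statement of no changes is wrong for that category.

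The practical effect is probably small and cannot be computed, because the documents give no AE rates. It is limited to AEs that begin between main-study consent and first dose and are still ongoing at dosing. Miscounting can go either way: an event that becomes serious without a grade change is missed, and an event that only improves is added.

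This rests on sites following the Protocol 11.3.1 recording rule. If they do not, more worsened events would be missed and fewer improving ones added. Safety summaries are descriptive and untested, so the primary analysis, sample size and type I error are unaffected. Confidence is high in the mismatch of text, and much lower in any visible change to the tables.

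**What to change.** 1. In SAP 3.5.1, define a TEAE as an AE that starts after the first dose, or a pre-dose AE that increases in severity grade or becomes serious after the first dose, as recorded on the eCRF.
2. State that a separate record showing only improvement of a pre-dose AE is not a TEAE.
3. Restore the worsened-AE summary of Protocol 12.4.4.2.1, or list its removal with a justification in SAP Section 6. If it is restored, state its reference point, since the protocol words it by study entry and not by first dose.

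The cost is a few sentences, one derivation rule and at most one added summary. Changes of severity category and seriousness are already collected under Protocol 11.3.1 and 11.3.2. The derivation does need the separate records of one event to be linked, which the documents do not describe and which should be checked against the eCRF. Within-grade worsening can be included only if the eCRF dates it.
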